8.2 Period of Observation

For the purpose of this study, the period of observation extends from the time the subject gives informed consent until 7 days (Day n+7) after the last administration for tolerance and for clinical outcome.

If the investigator detects or learns about a serious adverse event in a study subject after the end of the period of observation, and considers the event possibly related to prior study treatment, he or she should contact the sponsor to determine how the adverse event should be documented and reported.

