PROOF-OF CONCEPT STUDY TO INVESTIGATE THE IMPACT OF AZITHROMYCIN ADMINISTERED I.V. VS. PLACEBO ON THE PREVENTION OF PNEUMONIA IN VENTILATED PATIENTS COLONIZED WITH *PSEUDOMONAS AERUGINOSA*

Coordinating Investigator

[name], Paris

Centre xx

Principal Investigator

Department

Hospital

Address

City, mail code

Country

List of Centres by Country

Each country centre list will include:

- National Coordinating Investigator
- Each site with:
 - Site number
 - Principal Investigator
 - Subinvestigators
 - Address
- Quintiles Study Monitor(s)

Phase IIa

Multinational and multicentric

Indication

Prevention of pneumonia in ventilated patients colonized with *Pseudomonas aeruginosa*

Objectives

Primary objective

- To assess the clinical efficacy of azithromycin 300 mg i.v., used as a quorum-sensing blocker, compared to placebo for preventing or delaying the occurrence of pneumonia in ventilated patients colonized with *Pseudomonas aeruginosa*

Secondary objectives

- To assess other clinical efficacy variables
- To compare safety profile in target population
- To demonstrate using both *in vivo* and *in vitro* parameters whether azithromycin can be used clinically as a quorum-sensing blocker against *P. aeruginosa*
- To determine whether *P. aeruginosa* can develop resistance to the quorum-sensing blocker effect of azithromycin

- To check whether prolonged treatment with azithromycin may induce resistance to any of 11 antipseudomonal antibiotics (list in Section 6.2.)
- To verify whether emergence of resistance to other bacteriae may be elicited by assessing rate of infections in both study groups (azithromycin vs. placebo)

Design

2-parallel groups, double blind, randomized, placebo controlled, multiple i.v. dose administered once daily

Population

- Intubated patients
- Age 18 to 75 years
- Males and non pregnant females
- Respiratory tract colonized by *Pseudomonas aeruginosa* as documented by tracheal aspirate

Sample size

- Recruit a total of 120 to 240 patients in order to achieve 100 to 200 assessable cases
- Stop recruitment when 10 *P. aeruginosa* pneumonia cases have been documented and confirmed by panel of experts under blinded conditions

Treatments

- 300 mg azithromycin as i.v. solution at 2 mg/mL or saline (placebo), infused daily over 1 hour, until extubation (Day n-1), occurrence of pneumonia (Day x), exitus, or for a maximum of 20 consecutive days (Day 20)

Clinical efficacy (clinical site)

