7.1.1. Clinical efficacy data (collected at each clinical site)

Clinical efficacy (clinical site)

- Occurrence of *P. aeruginosa* pneumonia (primary variable)
The diagnosis of pneumonia will be assessed under blinded conditions by an independent panel of experts prior to stopping the study
- Occurrence of death (excluded if death within 3 days and not elicited by *P. aeruginosa*)
- Time to pneumonia, to exitus (Day -1), or to bacteremia
- Time to extubation (Day n-1)
- Overall outcome (until Day n+7)
- Duration of hospital and ICU stay
- Cost assessment
- PaO₂/ FI_{O2}
- Occurrence of infections to other bacterial strains

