- Body temperature (tympanic or rectal) ~17:00
- Local tolerance (24 hours)
- Systemic tolerance (24 hours)

Day 3

On the morning of Day 3, prior to infusion of test drug, the following procedures will be performed:

- Adverse events from previous night
- Local tolerance
- Body temperature (tympanic or rectal) ~7:00
- Blood pressure, heart rate, respiration rate (~8:00)

- Blood (see Appendix B)
 - Hematological profile
 - Blood chemistry
 - WBC, CRP
- Specimen for blood culture (only if clinically indicated)
- Blood gases
- Oxygenation: PaO₂/ FI_{O2}
- CPIS (use results of lung X-ray of same day whenever possible)
- Clinical endpoints
- Tracheal aspirate 1 (transfer to local laboratory, for parameters see Section 7.1.2 above)
 - Quantification of *P. aeruginosa* (CFU/mL)
 - Isolation of *P. aeruginosa* strain (storage -70°C)

After these activities, the test drug will be infused over 1 hour, usually from 8 to 9 o'clock.

Post treatment activities will include:

- ECG, 1 to 4 hours post infusion start
- Tracheal aspirate 2 (for freezing and transfer to Geneva laboratory for investigation), collected ~6 hours post infusion start
- Blood pressure, heart rate, respiration rate (~6 hours post infusion start)
- BAL if required medically
- Lung X-ray whenever possible during the day
- Body temperature (tympanic or rectal) ~17:00
- Local tolerance (24 hours)
- Systemic tolerance (24 hours)

Subsequent study days in 3 day cycles (Day 4, 5 & 6; Day 7, 8 & 9; Day 10, 11 & 12; etc.)

This same treatment and sampling policy, using a 3-day cycle will be used until Day n which may correspond to Day 21 (24 hours after last treatment day i.e. after 20 days of treatment), or to extubation day because mechanical ventilation is medically not required any longer, or to exitus day (due to underlying disease complication, infection due to any strain type and site with or without sepsis, *P. aeruginosa* infections of non pulmonary location) and finally to Day x when *P. aeruginosa* pneumonia diagnosed.

The procedures to be performed daily or every third day are summarized in the Study Schedule (page 10) and as briefly reviewed below:

Day 4, 5, 7, 8, 10, 11, 13, 14, 16, 17, 19	Correspond to Day 2
Day 6, 9, 12, 15, 18	Correspond to Day 3
Day x (pneumonia, see below)	Corresponds to Day 3 with some additional parameters and study drug is terminated once diagnosis confirmed
Day n-1 or Day 20	Corresponds to Day 3, and is last day of test drug (with some additional parameters)

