7.2.4. Day x (Day of pneumonia)

The day when a diagnosis of established pneumonia or possible pneumonia is made, will be called Day x. Treatment against *P. aeruginosa* pneumonia will be initiated as soon as the diagnosis is confirmed or if this pathogen is considered as a highly likely cause of pneumonia. The Day x procedures will be implemented as completely as possible on that day (similar to Day n-1) and the remaining items will be performed the next day (Day n). The patient will not receive the test drug on the following morning and the patient will be discharged from the study on Day n with safety and physical examination.

In case of suspicion of pneumonia the necessary explorations will be performed in order to lead to a confirmed diagnosis based on the criteria for *P.aeruginosa* summarized in the table presented below:

Investigation	Documented Pneumonia Day x
BAL	$\geq 10^4$ CFU/mL
Or tracheobronchial aspirate	$\geq 10^5$ CFU/mL
Or protected brush specimen (PBS)	$\geq 10^3$ CFU/mL
CPIS* (see detailed score in App. I)	≥ 6

The diagnosis of pneumonia will be confirmed at later stage under double blind conditions by a panel of independent clinical experts prior to stopping the study to ensure that 10 documented cases of *P. aeruginosa* pneumonia have been included in the study for assessment. The data provided will be patient characteristics, symptoms, all CPIS parameters generated, CPIS overall scores, all X-rays collected and results of BAL (or tracheobronchial aspirate or protected brush). Efforts will be made to achieve a total of 10 pneumonia cases in patients who do not receive concomitant therapy with an antibiotic with activity against the isolated *P. aeruginosa* strain, providing however the overall constraint for a maximum of 240 patients entered will not be trespassed.

Post treatment activities will include:

- Tracheal aspirate 2 (for freezing and transfer to Geneva laboratory for investigation), collected early afternoon (usually 6 hours [if Day x] or 30 hours [if Day n and if applicable] after last test drug administration) if patient still intubated and even if antipseudomonal antibiotherapy has been meanwhile initiated
- ECG, 1 to 4 hours late morning Day x
- Blood pressure, heart rate, respiration rate (early afternoon Day x or Day n)
- Lung X-ray whenever possible that day

- Body temperature (tympanic or rectal) ~17:00
- Local tolerance (up to 24 hours)
- Systemic tolerance (up to 24 hours)

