7.2.5 Day n-1 (last day of treatment)

Day n-1 is the last day of treatment and corresponds to:

- Day of extubation due to improvement of patient condition. If a patient has to be re-intubated within 24 hours he will remain in the study and treatment with study drug continued daily until 2nd extubation successful or until Day 20 of treatment whatever happens first
- Exitus day
- Day 20: Treatment with study drug will be stopped even if ventilation will be continued

The required tests will correspond to Day 3 requirements with additional items for discharge unless not feasible:

- Adverse events from previous night
- Local tolerance
- Body temperature (tympanic or rectal) ~7:00
- Blood pressure, heart rate, respiration rate (~8:00)
- Blood gases
- Oxygenation: Pa_{O2}/ FI_{O2}
- Tracheal aspirate #1, collected pre last dose early morning if patient still ventilated for transfer to local laboratory for:
 - Quantification of *P. aeruginosa*
 - Isolation of *P. aeruginosa* strain and storage at -70°C
 - Special Day n-1 assessment for MIC on *P. aeruginosa* strain with 11 antipseudomonal antibiotics (listed under Section 6.2)
- ECG 1-4 hours post drug
- Lung X-ray whenever possible that day
- CPIS (use lung X-ray of same day)
- Clinical endpoints
- APACHE II score
- Tracheal aspirate #2 (for freezing at -70°C and transfer to Geneva laboratory for investigation), collected 6 hours post drug or earlier if extubation planned
- Extubate if applicable, if possible in the afternoon and after collection of tracheal aspirate sample 2, as medically indicated by weaning procedures
- Store ventilation device in sterile pouch at -70 °C, pending shipment to Geneva laboratory

In the case of exitus, the examinations performed on the previous day and on last third day (Day 9, 12, 15 etc.) will be used as Day n-1 values and the respiration device will be recovered and stored as described above.

On **Day n**, no study drug will be administered and the patient will be discharged from the study after physical examination and after collecting blood and urine safety samples. Ventilation will be continued if required.

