7.2.6 Poststudy (Day n + 7)

Information on the patient outcome (pneumonia, infection, strain, etc.) and intercurrent adverse events over the past week will be collected one week after cessation of therapy, i.e. on Day n+7, even for patients treated with antipseudomonal antibiotherapy, whether ventilated or not. This information will be best achieved by the treating physician visiting the patient at his present location or by obtaining a report.

The Quintiles study monitor will control the labeling, storage, and coordinate the shipment of all biological samples collected during the study by the ICU nurse to the University Hospital of Geneva, Switzerland. Shipment will be performed in batches of patients when convenient for site, monitor, and Geneva laboratory (see Appendix G).

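### Death and overall outcome have no common follow-up day: collection of new events stops at Day n+7, counted from a last dose that the patient's own outcome sets

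*Protocol*

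**What the plan says.** **End of observation.** Section 8.2 states that the "period of observation extends from the time the subject gives informed consent until 7 days (Day n+7) after the last administration", for both tolerance and clinical outcome. Section 7.1.1 lists "Overall outcome (until Day n+7") as an efficacy variable. Section 7.2.6 provides one post-study contact, at which outcome and adverse-event information "will be collected one week after cessation of therapy, i.e. on Day n+7".

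**What sets the last dose.** The synopsis has treatment given "until extubation (Day n-1), occurrence of pneumonia (Day x), exitus, or for a maximum of 20 consecutive days (Day 20"). Section 7.2.5 says "Day n-1 is the last day of treatment and corresponds to" extubation, death or Day 20. For pneumonia, Section 7.2.4 says "The patient will not receive the test drug on the following morning and the patient will be discharged from the study on Day n". Section 7.2.3 says of Day n that it is a day "which may correspond to Day 21 (24 hours after last treatment day i.e. after 20 days of treatment").

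**The death variable.** Section 7.1.1 lists "Occurrence of death (excluded if death within 3 days and not elicited by" *P. aeruginosa*). No end day is attached to it. No section fixes a follow-up day counted from randomisation or Day 1 for death, infections or overall outcome.

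**The concern.** The events that close a patient's window (pneumonia, extubation, death) are themselves efficacy variables in Section 7.1.1. Length of follow-up is therefore a post-randomisation outcome. A patient who does well and is extubated early is watched for a shorter calendar time than one who stays ventilated to Day 20, and so is a patient who develops pneumonia early.

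A yes/no count of deaths over such windows does not estimate risk by any stated day. If the drug shifts pneumonia or extubation, the arms also differ in how long they are watched. Preventing pneumonia lengthens the azithromycin windows and can look like harm on death, infections and adverse events. Faster extubation shortens them and can look like benefit. Deaths and infections that are never collected cannot be restored by any later analysis.

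**Working it through.** **1. Day arithmetic.** Let the last dose be on Day L. Sections 7.2.3 and 7.2.5 make L = n-1, so n = L+1 and Day n+7 = Day L+8. Check against the protocol's own figure: L = 20 gives Day n = 21, as Section 7.2.3 states. Section 8.2 equates Day n+7 with 7 days after the last dose, which would be Day L+7.

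| Last dose (L) | 7 days after last dose | Day n+7 |
|---|---|---|
| Day 1 | Day 8 | Day 9 |
| Day 5 | Day 12 | Day 13 |
| Day 10 | Day 17 | Day 18 |
| Day 20 | Day 27 | Day 28 |

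The two definitions differ by one day throughout. Section 7.2.6 could be read consistently if cessation means Day n, but Section 8.2 refers to the last administration.

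**2. Range of windows.** Section 11.2 requires at least 5 days of treatment before extubation for the clinical analysis. Extubated patients in that set therefore have windows from Day 13 to Day 28, and one extubated on Day 5 has 28 - 13 = 15 days unobserved before Day 28. The safety set needs only one dose, so its windows can end on Day 9. Section 11.2 states no minimum for patients whose dosing is ended by pneumonia.

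**3. Effect on a single patient's observed risk.** Assume a constant death hazard, the same in both arms, set by an assumed 28-day mortality m: h = -ln(1-m)/28, and observed risk = 1 - exp(-h(L+8)). The protocol gives no figure for m, so a range is shown.

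| Assumed m | Last dose Day 5 (window 13) | Last dose Day 20 (window 28) |
|---|---|---|
| 20% | 9.8% | 20.0% |
| 30% | 15.3% | 30.0% |
| 40% | 21.1% | 40.0% |

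**4. Effect between arms, with no drug effect on death.** This was simulated with 1,000,000 patients per arm, exponential times to extubation, pneumonia and death, dosing capped at Day 20, and no efficacy-set restriction. All rates are assumptions.

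- *Drug only speeds extubation* (mean 10 days to 7 days; pneumonia 1% per day in both arms). The mean window falls from 16.5 to 14.7 days. Observed deaths go from 12.2% to 10.9%, 18.7% to 16.9%, and 25.5% to 23.2% for m = 20%, 30% and 40%. This is a false benefit of 1.3, 1.8 and 2.3 points.
- *Drug only prevents pneumonia* (1.5% per day against 0; mean extubation 10 days). In the untreated arm this gives 0.015/0.115 × (1 - exp(-0.115 × 20)) = 11.7% pneumonia, inside the 10 to 15% of Section 11.5. The mean window rises from 16.3 to 17.1 days. Observed deaths go from 12.1% to 12.6%, 18.4% to 19.3%, and 25.2% to 26.2%. This is a false harm of 0.5, 0.9 and 1.0 points.

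**5. Ceiling on the pneumonia route.** The best case in Section 11.5 is 10 pneumonias in 100 placebo patients against 0 in 100. If every case fell on Day 1 and would otherwise have been dosed to Day 20, the mean gap in last-dose day is 0.10 × 19 = 1.9 days.

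**6. Same horizon for all.** Counting deaths to Day 28 for every patient, the simulated arms agree apart from simulation noise.

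**The case against.** **The arms balance unless the drug acts.** This stands. Windows are certain to differ between patients. They differ between arms only if azithromycin changes pneumonia, extubation or survival. A reader might infer that the arms are bound to be compared over unequal periods, or in a known direction; the documents support neither. The trial's premise in Section 1.1 is, however, that delaying pneumonia lets patients reach extubation first.

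**Pneumonia cases are followed further.** This also stands in part. A reader might infer that observation of pneumonia patients simply stops about a week later, hiding much of the roughly 40% mortality that Section 1.1 gives for ventilator-associated pneumonia. But Section 8.1.1 makes pneumonia an adverse event, and Section 8.3 requires adverse events to be followed to outcome, beyond the observation period if needed. That follow-up ends at the investigator's discretion and covers events already recorded. Section 8.2 adds only later serious events thought possibly related. Neither collects new deaths or infections in all patients.

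**The distortion is small.** True. A mean gap of 2 days or more might be assumed, but the protocol's own 10% against 0% scenario caps the pneumonia route at 1.9 days, and no figure is given for an effect on extubation. At 21% mortality the standard error of the difference is √(2 × 0.21 × 0.79/100) = 5.8 points with 100 per arm and 8.1 with 50. Nor is an extubation on Day 3 a fair example for efficacy, since Section 11.2 excludes it from that set.

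**Analysis could adjust.** Time-to-event variables are listed, and a statistical plan is announced in Section 11.3. But censoring a week after extubation or pneumonia depends on the patient's state, and no plan recovers events that were not collected.

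**Conclusion.** The point holds as a design weakness in secondary and safety outcomes. Occurrence of death and overall outcome lack a common day from randomisation, and the windows run from about Day 13 to Day 28 for extubated patients in the efficacy set, and from as early as Day 9 in the safety set. The length of each window is certain from the text. A difference between arms is conditional on a drug effect, can go in either direction, and under the assumed constant hazards comes to roughly 0.5 to 2 points on death. The comparison of *P. aeruginosa* pneumonia by Fisher's exact test is not the main concern. The one-day conflict between Section 8.2 and the day definitions is a plain inconsistency. Because the remedy is simple, this is a cheap improvement rather than a serious flaw.

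**What to change.** Add one status check at Day 28, counted from Day 1, for every randomised patient whatever ended treatment. It should cover vital status, ventilation status, and pneumonia or other infection since Day n. Define occurrence of death and overall outcome at Day 28. Keep Day n+7 as the adverse-event contact.

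Reconcile Sections 7.2.3, 7.2.5, 7.2.6 and 8.2 so that the contact day and its stated distance from the last dose agree.

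The cost is one chart check or call per patient, and tracing of some who have been transferred. Day 28 is already the latest possible Day n+7, so maximum follow-up does not lengthen. Section 8.1.2 expects patients to stay in hospital 2 to 4 weeks after study completion. For one extubated on Day 5 (Day n = 6) that is Day 20 to Day 34, so many will still be inpatients. Section 7.2.6 already accepts a report in place of a visit.

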8.3 Documentation and Reporting of Adverse Events by Investigator

All adverse events that occur after the subject has signed the informed consent document must be documented on the pages provided in the CRF.

The following approach will be taken for documentation:

- **All non serious adverse events** must be documented on the “Adverse event” page of the CRF (systemic, local if considered clinically significant, biological if considered clinically significant)
- **All serious adverse events** must be documented on the “Serious adverse event form” which will be part of the CRF (basic report and updates). The information will be forwarded to the monitor and to the identified sponsor’s representatives **within 24 hours, or at the latest on the following working**

day, by telephone and by Fax.. The sponsor's representatives will ensure that all legal reporting requirements are met.

Every attempt should be made to describe the adverse event in terms of a diagnosis, and not as a list of symptoms. If appropriate, component symptoms should also be listed below the diagnosis, as comments. Non-specific signs or symptoms may be recorded as a diagnosis. Assessing the relationship to study drug or to study conditions must be performed and rating of intensity provided (definitely not, possibly, probably, not assessable).

The initial serious adverse event report must be as complete as possible, including details of the current illness and (serious) adverse event, and an assessment of the causal relationship between the event and the study medication. Information not available at the time of the initial report (e.g., an end date for the adverse event, laboratory values or investigation results received after the report) must be documented on a follow-up "Serious adverse event" form.

All subjects who have adverse events, whether considered associated with the use of the study medication or to study conditions or not, whether non serious or serious, must be monitored to determine the outcome. The clinical course of the adverse event will be followed up according to accepted standards of medical practice, even after the end of the period of observation, until a satisfactory explanation is found or the investigator considers it medically justifiable to terminate follow-up. Should the adverse event result in death, a full pathologist's report should be supplied, whenever possible.

All questions on the completion and supply of adverse event report forms and any further forms issued to the investigator at a later date to clarify unresolved issues should be addressed to the sponsor.

Overdose is unlikely to occur in this study since the study drug (300 mg or 0 mg in 250 mL saline) is administered by the ICU staff under the investigator's responsibility, as 1 pouch per study day prepared by the hospital pharmacist and infused i.v. at 250 mL/hr i.e. at a concentration of 1.2 mg/mL which is well tolerated. In case of overdose and from a systemic point of view, GI symptoms may occur which are related in terms of incidence and intensity to total dose given, and from a local point of view, pain and irritation at study site may occur if delivery speed would be at 500 mL/hr or above.

9. WITHDRAWALS

9.1 Withdrawal of Subjects

Patients may be withdrawn from study medication for the following reasons:

- At their own request or at the request of their legally authorized representative
- If, in the investigator's opinion, continuation in the study could represent a risk or could be detrimental to the subject's well-being
- At the specific request of the sponsor's representatives

In all cases, the reason for withdrawal must be recorded in the CRF and in the subject's medical records. The subject must be followed up to establish whether the reason was an adverse event, and, if so, this must be reported in accordance with the procedures in Section 8.3.

As far as possible, all examinations scheduled for the final study day must be performed on all subjects who receive study medication but do not complete the study according to protocol (see Section 7.2). The investigator must make every effort to contact subjects lost to follow-up.

